### 2.2. Duration of exposure: censored & non-censored

The incidence rate for a patient is derived from the duration of exposure to treatment of that patient. When averaging incidence rates, a patient's duration of exposure is given either A) by the time when the event has occurred (non-censored data), or B) by the total duration of treatment in case the patient does not show the adverse event in question (censored data). Depending on whether a patient has an adverse event or not, the duration of exposure enters the denominator in its non-censored or censored form, respectively.

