Bone marrow aspirate ¹	Per Amend 6: Bone marrow testing to be performed at local laboratory. Morphology and additional diagnostic tests (including local Cytogenetics by FISH)	X ^h	At least every 2 years and at suspected CR. See Table 10 for details.							X		

Notes	Active Monitoring (Arm A; 12-week disease evaluations) / Treatment Phase (Arm B; 4-week treatment cycles after Cycle 6) ^a (up to 39 cycles or 36 months, whichever occurs first)	End of Active Monitoring/ End of Treatment	Pre-PD Follow-up	PD	Post-PD Follow-up							
Imaging and Additional Studies												
Lytic lesion assessment by low-dose whole body computed tomography (preferred), PET-CT, or CT (central read) ^{d,l}	Use same methodology throughout study. Per Amend 6: to be read by local radiologist.	X (within 56 days before randomization)	Every 12 months until confirmed PD									
Focal lesion assessment by magnetic resonance imaging (central read) ^{d,l}	Spine and pelvis magnetic resonance imaging. Per Amend 6: to be read by local radiologist.	X (within 56 days before randomization)	Every 12 months and at biochemical progression or at suspected PD									
Patient Reported Outcomes ⁱ (EORTC QLQ-C30, EORTC QLQ-MY20, and EQ-5D-5L)	To be collected after the subject signs informed consent and before any interventions scheduled for the same day as the PRO assessments are collected	X	Week 12, Week 24, and Week 60 (with disease evaluations), then every year until the end of the Treatment/Active Monitoring Phase (with disease evaluations).			X ^m	Every year until the end of the study or PD.					
Medical Resource Utilization	See Section 9.6	At disease assessment visits										
Ongoing Subject Review												
Adverse Events		Active Monitoring (Arm A): Continuous from the time of signing of ICF until 36 months from the start of active monitoring or until start of next therapy, whichever is earlier Daratumumab (Arm B): Continuous from the time of signing of ICF until 30 days after last daratumumab dose, or until start of next therapy, whichever is earlier										
Concomitant Medications		Active Monitoring (Arm A): Continuous from the time of signing of ICF until 36 months from the start of active monitoring or until start of next therapy, whichever is earlier										

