## **4.4. Extent of Exposure**

Extent of exposure to study drug will be summarized and presented on safety analysis set.

Treatment duration and the total number of treatment cycles will be summarized descriptively. The number and percentage of subjects treated within each cycle will also be summarized for the dara-SC subjects.

Treatment duration in months is derived as last non-zero daratumumab dosing date – first non-zero daratumumab dosing date + 1 and then divided by 365.25/12. The maximum number of treatment cycles for each subject is the largest cycle number in which a subject receives any non-zero dose of daratumumab.

Total dose (mg) for Dara group is defined as the sum of total dose (mg) administered and recorded on CRF at each visit. Descriptive statistics for the total daratumumab dose received and total number of injections will be provided.

Dose intensity, which is defined as the sum of total dose administered in all cycles divided by the number of treatment cycles, will be calculated and summarized for daratumumab treatment

group. Additionally, the daratumumab dose intensity will be summarized by Cycle during the treatment.

Relative dose intensity (%), which is defined as the ratio of total dose received and total planned dose (calculated as the planned dose level times the number of administered injections), will be calculated and summarized for each treatment group. Additionally, the relative dose intensity will be summarized by Cycle during the treatment.

The incidences of dose delays and corresponding reasons will be provided. The frequencies of actions planned prior to injection start and taken during injection will be summarized, together with reasons reported on eCRF. In addition, a summary of dose delays will also be provided by cycle during the treatment.

The treatment label identifier dispensed by each subject will be listed.

A separate listing including all daratumumab injection data will also be provided.

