### **6.1. Adverse Events**

AEs will be recorded in standard medical terminology and graded according to the National Cancer Institute Common Terminology Criteria for Adverse Events (NCI-CTCAE), Version 4.03. For AE reporting, the verbatim term used in the CRF by investigators to identify adverse events will be

coded using the latest version of Medical Dictionary for Regulatory Activities (MedDRA) coding dictionary.

The relationships to study medication will be recorded as not related, doubtful, possible, probable, or very likely on eCRF for all the AEs. Adverse events will be categorized and summarized according to their highest relationship to study medication. An adverse event is considered as related to study medication if the relationship is recorded as possible, probable or very likely.

For subjects treated with daratumumab, treatment-emergent adverse events (TEAEs) are defined as any AE with onset date and time on or after that of the first dose through 30 days after the last study drug administration, or the day prior to start of subsequent therapy, whichever is earlier; or the follow-up AE (linked to an existing TEAE) with onset date and time beyond 30 days after the last study agent administration but prior to the start of subsequent therapy; or any AE that is considered related to (very likely, probably, or possibly related) study medication regardless of the start date of the event. AEs with missing or partial onset date and time will be considered as treatment-emergent unless the onset date and time of an AE can be determined as earlier than that of the first dose, or later than 30 days after last study drug administration. For subjects on active monitoring, treatment-emergent adverse events will be defined as AEs that occur after randomization and prior to start of subsequent therapy, or prior to discontinuation from the study or if the subject continues on study for 3 years, then up to 30 days after that, whichever is earlier.

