### 2.6.3. Average EAIR on a global level

The average  $EAIR$  on a global level considers the overall first event per patient only, and only one (the corresponding) exposure time in the denominator (confer before, where the denominator in the  $EAIR_{SOC}$  depends on the overall number of PTs):

$$EAIR_{global} = \frac{\sum_{i=1}^n TEAE_i}{\sum_{i=1}^n t_i},$$

whereby  $TEAE_i$  represents the first TEAE among all TEAEs of patient  $i$  and  $t_i$  as before (time when TEAE occurs (non-censored data) or total duration of treatment if no event occurs (censored data))

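### The exploratory EAIR stops the clock for event-free Arm B subjects at the last dose while events count for up to 30 days more, and it defines no time at risk for Arm A

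*SAP*

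**What the plan says.** SAP Attachment 1, 2.2 takes treatment exposure as the time base: "The incidence rate for a patient is derived from the duration of exposure to treatment of that patient". A subject with the event contributes the time to the first event. A subject without it contributes time given "by the total duration of treatment in case the patient does not show the adverse event in question". Attachment 1, 2.4 repeats the rule, and 2.6.3 repeats it for the global rate: "total duration of treatment if no event occurs (censored data".

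Attachment 1 does not define that duration. The one definition in the SAP is in 4.4, Extent of Exposure: "last non-zero daratumumab dosing date – first non-zero daratumumab dosing date + 1", converted to months.

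The events come from SAP 6.1. In Arm B a TEAE has its onset "on or after that of the first dose through 30 days after the last study drug administration", or before subsequent therapy starts if that is earlier. Follow-up events linked to a TEAE can count later than 30 days, and drug-related events count with no time limit. In Arm A the window opens at randomization. It closes at subsequent therapy, at study discontinuation, or 30 days after 3 years on study, whichever is first.

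Protocol Table 1 collects Arm A adverse events only "until 36 months from the start of active monitoring or until start of next therapy, whichever is earlier". Protocol Section 6 states that Arm A gets no study medication. Arm A is nevertheless in the safety analysis set (SAP 2.3.2), and Attachment 1, 2.1 suggests a t-test-like comparison of the rates between arms.

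**The concern.** An incidence rate needs the same window in numerator and denominator. Here, an Arm B subject whose first event falls on day 20 after the last dose adds one event, and adds time that includes those 20 days. A subject observed event-free through the same 20 days adds none of them. Person-time is therefore short and the Arm B rate is too high. The relative shortfall is larger when treatment is shorter.

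In Arm A the denominator refers to something that does not exist. An EAIR is computed so that arms observed for different lengths of time can be compared, and that comparison cannot be programmed from the text. Someone will have to choose an Arm A rule, and the choice can move the rate ratio far more than the 30-day gap does.

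**Working it through.** The documents state no EAIR, adverse event rate or total exposure, so there is no figure of the plan's own to reproduce.

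**Inputs**
- Last scheduled dose: Cycle 39 Day 1 (SAP 1.2). By the formula in SAP Table 2 this is study day (39 − 1) × 28 + 1 = 1065.
- Treatment duration under SAP 4.4: T = 1065 days. One month is 365.25/12 = 30.4375 days, so T = 35.0 months.
- Arm B TEAE window (SAP 6.1): W = T + 30 = 1095 days, or 36.0 months, if no subsequent therapy starts first.
- Assumption: a constant event hazard λ, equal in both arms, so that the true rate ratio is 1.

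**Step 1. Rare event, Arm B.** Nearly all person-time comes from event-free subjects, so the rate as written divided by the true rate is (T + 30)/T. The shorter durations are illustrative.

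| T (days) | (T + 30)/T | Excess |
|---|---|---|
| 1065 (39 cycles) | 1095/1065 | 2.8% |
| 730 (24 months) | 760/730 | 4.1% |
| 365 (12 months) | 395/365 | 8.2% |
| 169 (last dose on Cycle 7 Day 1) | 199/169 | 17.8% |

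The EAIR is a pooled sum over a sum, so mean T governs the arm-level excess. Assume that treatment stops at the planned 48-month median PFS rate (ln 2/48 = 0.01444 per month), capped at 35 months. Mean T is then (1 − e^(−0.01444 × 35))/0.01444 = 27.5 months, or 836 days, and the excess is 30/836 = 3.6%. Add 10% per year for other discontinuation (−ln 0.9/12 = 0.00878, total 0.02322 per month). Mean T is then 24.0 months, or 729 days, and the excess is 30/729 = 4.1%.

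**Step 2. Commoner events, completers.** With incidence p over the window, λ = −ln(1 − p)/W. True person-time per subject is p/λ; as written it is p/λ − 30(1 − p).
- p = 0.10: 1039.3 days against 1039.3 − 27 = 1012.3; ratio 1.027.
- p = 0.30: 921.0 days against 921.0 − 21 = 900.0; ratio 1.023.

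The excess shrinks as incidence rises, so the figures in Step 1 are ceilings for a given T.

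**Step 3. Between arms.** Arm B is as written, all subjects complete, and p = 0.10 in Arm B. The Arm A window in SAP 6.1 is 36 × 30.4375 + 30 = 1125.75 days.

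| Rule substituted for event-free Arm A subjects | B/A (true value 1) |
|---|---|
| Full SAP 6.1 window | 1.027 |
| Time cut at 36 months, events counted 30 days longer | 1.001 |
| Time and events both stop at 36 months (Table 1) | 1.027 |
| Zero, since no treatment was given | 0.055 |

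In the second row the two arms carry nearly the same error and it cancels. In the last row only subjects with an event contribute time, and the Arm A rate is inflated about 19-fold. For that rule the ratio is 0.027 at 5% incidence and 0.18 at 30%.

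**The case against.** **The last-dose reading is an inference.** Attachment 1 does not cite SAP 4.4. For by-cycle analyses, SAP 2.1 ends the last cycle at the end-of-treatment visit, which the protocol places 30 (±3) days after the last dose. On that date the gap would nearly vanish. It stands that the link to 4.4 is not written down. But SAP 2.1 defines the end of a cycle, not a treatment duration, and 4.4 is the only definition of the latter. If 4.4 is set aside, the term is undefined in both arms and the remedy is the same.

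**A reader might infer that the plan inflates Arm B relative to Arm A.** The documents do not support this. With no Arm A rule, the ratio can come out near 1.03, near 1.00 or far below 1. Protocol 10.1 does speak of completing study treatment after 36 months of monitoring, which makes a 36-month Arm A time a natural guess. That is a completion rule, however, and gives no time at risk to a subject who leaves earlier.

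**A reader might also infer that the 30 days are credited to every subject with an event.** They are not. An early event contributes only its own time; post-dose days enter only when the first event falls in them.

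**The figures may be too large.** This stands. Many who stop treatment will have progressed, and if they start subsequent therapy within 30 days the window closes sooner.

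**It is exploratory, and an exposure-based rate is the stated intent.** The first part is correct: the analysis sits in the HEMAR attachment and the Section 6 safety tables do not use it. The second does not settle the matter, because event times after the last dose are not exposure under 4.4 either. The rule as written mixes two time bases.

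**Conclusion.** The point holds for Arm B in a fixed direction. As written, the rate is overstated by up to about 2.8% for a rare event when 39 cycles are given, about 4% at 24 months of treatment and about 8% at 12 months. This rests on the SAP 4.4 definition applying, on a constant hazard, and on the full 30 days being available. For Arm A, the finding is that no denominator is defined. Any distortion between the arms has no determinable size or direction until one is. The missing Arm A rule is potentially the larger defect, because a literal reading gives its event-free subjects no time at all.

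The importance is low. Nothing here reaches PFS, the secondary tests or alpha, and a few percent on an exploratory rate would be unlikely to change a safety conclusion. It is still a rule that yields a wrong rate rather than a mere omission of detail, and it is easy to correct.

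**What to change.** In SAP Attachment 1, 2.2, 2.4 and 2.6.3, replace treatment duration with time at risk over the arm's own TEAE window in SAP 6.1, ending at the first event if there is one.
- **Arm B:** from first dose to the earliest of 30 days after the last dose, the day before subsequent therapy, death, study discontinuation or data cut-off.
- **Arm A:** from randomization to the earliest of the day before subsequent therapy, study discontinuation, death, data cut-off or the SAP 6.1 end of 3 years plus 30 days.

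Before fixing the Arm A end, reconcile it with protocol Table 1, which stops Arm A collection at 36 months. Cutting the denominator at 36 months while SAP 6.1 still admits events for 30 days more would recreate the mismatch in the other arm. Events and time must share one end date.

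Leave out of the EAIR numerator any linked or related event with onset after the window. The hazard ratios and Kaplan-Meier curves in the attachment's additional time-to-event section state no censoring time, and could cite the same definition.

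The cost is one definition in the attachment. The dates needed are already collected, and no new data are required.

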## 2.3. Incidence rate per patient

The incidence rate for a specific event of a patient  $i$  is the reciprocal of time  $t$  when the first event occurs:

$$EAIR_i = \frac{1}{t_i}.$$

## 2.4. Average EAIR

The  $EAIR$  averaged over all patients is

$$EAIR = \frac{\sum_{i=1}^n TEAE_i}{\sum_{i=1}^n t_i},$$

whereby

- a) a TEAE enters the sum in the nominator unweighted ( $TEAE_i = 1$ , otherwise  $TEAE_i = 0$ ), and
- b) the duration of exposure enters the denominator as described before:  $t_i = \begin{cases} \text{time of TEAE} & \text{if occurring (non-censored data)} \\ \text{total duration of treatment} & \text{if no event occurs (censored data)} \end{cases}$

## 2.5. EAIRs on the level of a SOC and on the global level on a 'per-PT' basis

### 2.5.1. Average EAIR per PT

The  $EAIR$  for a specific PT is an average over all patients, i.e.

$$EAIR_{PT} = \frac{\sum_{i=1}^n TEAE_{PT,i}}{\sum_{i=1}^n t_{PT,i}},$$

whereby the number of TEAEs and durations of exposure enter the nominator and the denominator.

### 2.5.2. Average EAIR per SOC

The average  $EAIR$  per SOC considers the first event of each patient within the SOC. The denominator includes the exposure time of each adverse event of all PTs within the SOC, per patient, i.e.

$$EAIR_{SOC} = \sum_{i=1}^n TEAE_{SOC,i} \sum_{PT=1}^{n \text{ PTs per SOC}} \frac{1}{t_{PT,i}},$$

where  $TEAE_{SOC,i}$  is the first event per patient per SOC and  $t_{PT,i}$  is the exposure time for a specific preferred term of a given patient.

Note: This  $EAIR$  is an incidence rate per *average (or typical)* preferred term in that SOC (cf. 3.6.1).

### 2.5.3. Average EAIR on a global level

The average  $EAIR$  on a global level only considers the first event per patient across all events. The denominator includes the exposure times of all PTs, i.e.

$$EAIR_{global} = \sum_{i=1}^n TEAE_i \sum_{PT=1}^{n_{PTs}} \frac{1}{t_{PT,i}},$$

where  $TEAE_i$  is the first event of a patient overall and the  $t_{PT,i}$ 's are PT-specific exposure times of that patient.

Note: This EAIR is an incidence rate *per average (or typical)* preferred term.

## 2.6. Second analyses

### 2.6.1. Average EAIR per PT

The  $EAIR$  for a specific PT is an average over all patients as described before, i.e.

$$EAIR_{PT} = \frac{\sum_{i=1}^n TEAE_{PT,i}}{\sum_{i=1}^n t_{PT,i}},$$

whereby the number of TEAEs and durations of exposure enter the nominator and the denominator.

### 2.6.2. Average EAIR per SOC

The average  $EAIR$  per SOC considers the first event per patient per SOC only, and only one (the corresponding) exposure time in the denominator (confer before, where the denominator in the  $EAIR_{SOC}$  depends on the number of PTs per SOC):

$$EAIR_{SOC} = \frac{\sum_{i=1}^n TEAE_{SOC,i}}{\sum_{i=1}^n t_{SOC,i}},$$

Note: This EAIR is an incidence rate *per SOC*.

### 2.6.3. Average EAIR on a global level

The average  $EAIR$  on a global level considers the overall first event per patient only, and only one (the corresponding) exposure time in the denominator (confer before, where the denominator in the  $EAIR_{SOC}$  depends on the overall number of PTs):

$$EAIR_{global} = \frac{\sum_{i=1}^n TEAE_i}{\sum_{i=1}^n t_i},$$

whereby  $TEAE_i$  represents the first TEAE among all TEAEs of patient  $i$  and  $t_i$  as before (time when TEAE occurs (non-censored data) or total duration of treatment if no event occurs (censored data))

## 3. ADDITIONAL TIME TO EVENT ANALYSES

In case of different exposure times, time adjustment for AE is necessary. Hazard Ratio and Kaplan-Meier curves will be conducted including number of patients at risk for the following safety endpoints:

- Any TEAE
- Any Serious TEAE

- Any TEAE leading to death
- Any Grade 3 or 4 TEAE
- Any Grade 3 or higher TEAE
- Any TEAE leading to treatment discontinuation

Detailed description by preferred term:

- TEAEs by preferred term with prevalence $\geq 10\%$
- Grade 3 or 4 TEAEs preferred term with prevalence $\geq 5\%$
- Grade 3 or higher TEAEs by preferred term prevalence $\geq 5\%$
- Serious TEAEs preferred term with prevalence $\geq 2\%$
- TEAEs leading to treatment discontinuation preferred term with prevalence $\geq 1\%$
- TEAE leading to death preferred term without prevalence cut-off

### **3. MEDICAL RESOURCE UTILIZATION**

Medical resource utilization (excluding study injection administration) will be descriptively summarized by treatment group. Frequencies of hospitalization, outpatient visits, type of hospitalization or outpatient visit, reasons for hospitalization or outpatient visit, durations of hospitalization or outpatient visit will be calculated and tabulated.

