
Table 1: Time and Events Schedule
 
9.2 Efficacy Evaluations
 
9.2.3 CRAB Criteria-related Laboratory Assessments
 
9.2.4 Myeloma Protein Measurements in Serum and Urine
 
9.2.5 β2-microglobulin and Lactate Dehydrogenase
 
9.2.6 Bone Marrow Examination
 
Assessment of Bone Disease
 
9.7 Safety Evaluations
 
9.5 Patient-reported outcomes
 
9.6 Medical Resource Utilization
	
Central laboratory testing will be discontinued.
 
Pre-PD follow up and PD assessments:
 
 • Disease evaluations should continue according to Time & Events Schedule, by local assessment • Only disease progression by investigator via local assessment will be reported to the Sponsor. • Assessment of response for disease evaluations and local laboratory and imaging results will not be reported to the Sponsor. 
Post-PD follow-up:
 
PRO and MRU collection at Months 12 and 18 in the have been discontinued.
	
Post primary analysis, central laboratory testing and central imaging are no longer required.
 
Post primary analysis, PRO and MRU collection at Months 3 and 6 are considered sufficient.

Table 1: Time and Events Schedule
 
9.4 Biomarkers
 
Table 10
	
Central Laboratory Biomarker assessments will be discontinued.
	
Post primary analysis, biomarker analyses are no longer required.

9.3 Pharmacokinetics and Immunogenicity
	
Immunogenicity and PK assessments will no longer be collected.
	

SYNOPSIS
 
Table 1: Time and Events Schedule
 
Table 2: Daratumumab Administration (Arm B Only)
 
9.1.1 Overview
 
9.2 Efficacy Evaluations
 
9.3.2 Analytical Procedures
 
9.4 Biomarkers
 
9.5 Patient-reported Outcomes
 
9.6 Medical Resource Utilization
	
Home health care visits have been removed throughout the protocol.
	
Home health care visits are no longer available.
 
NOTE: Tele health visits (conducted via phone or video conference) may continue as deemed necessary.

11.12 Data Monitoring Committee
	
The IDMC will be discontinued once the primary analysis endpoint has been achieved.
	
IDMC will no longer be required.

Throughout the protocol
	
Minor grammatical, formatting, or spelling changes were made.
	
Minor errors were noted.

SYNOPSIS

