9.2. Efficacy Evaluations

Disease assessments will be performed every 12 weeks until PD. A window of ± 7 days around the scheduled assessment date is allowed. For subjects with treatment delays, disease assessments should be performed at the scheduled disease assessment dates. They do not need to be repeated at the time of delayed daratumumab administration. Disease progression, if based on laboratory results only, must be confirmed by a consecutive assessment. A repeated investigation for confirmation of disease progression does not need to occur within a specified timeframe and could potentially occur on the same date (at a later timepoint). However, the original value meeting disease progression and the confirmation value must be consecutive (ie, no intermediate values that do not meet the definition of disease progression). It is not a requirement to have a repeat investigation if disease progression is based on at least 2 of the laboratory tests of Hb, calcium,

renal function and FLC at the same assessment date (eg, when Hb <10 g/dL and creatinine clearance <40 mL/min are present on the same day).

Disease assessments will be performed according to the Time and Events Schedule ([Table 1](#)). Disease evaluations scheduled for treatment days should be collected before study drug is administered. Disease progression to MM will be evaluated using the IMWG diagnostic criteria for MM ([Table 9](#)) (Rajkumar 2014²⁹). For subjects who discontinue active monitoring (Arm A) or daratumumab (Arm B) before PD, disease assessments should be performed according the Time and Events Schedule ([Table 1](#)) until study completion or confirmed PD (or other reasons as outlined in [Section 10](#)).

Per protocol Amendment 6, disease assessments will only be performed locally and locally diagnosed disease progression will be reported based upon study investigator review per IMWG criteria.

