9.6. Medical Resource Utilization

Medical resource utilization data associated with medical encounters (including tele-health visits [conducted via phone or video conference]), will be collected in the eCRF by the investigator and study-site personnel for all subjects at the disease assessment visits and at Months 3 and 6, post-PD. Protocol mandated procedures, tests, and encounters are excluded. The data collected will be

used to conduct exploratory analyses that may be used to support the value story and cost-effectiveness modelling for market access. The data collected include:

- Number and characteristic of diagnostic and therapeutic tests procedures (inpatient and outpatient)
- Number and duration of hospitalization (total length of stay [days], including duration by each hospital unit (intensive care unit)
- Outpatient medical encounters (including physician, nurse practitioner or emergency room visits, tests and procedures)

Please see eCRF completion guidelines for more details.

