11.9. Medical Resource Utilization Analyses

Medical resource utilization will be summarized descriptively by treatment group. Additional analyses may be conducted; details and results of any additional analyses will be presented in a separate report.

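### Medical resource use is observed for a time that depends on progression, but the plan summarises it by arm with no person-time denominator and no split at progression

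*SAP*

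**What the plan says.** Protocol 9.6 has MRU recorded by the investigator and "study-site personnel for all subjects at the disease assessment visits and at Months 3 and 6, post-PD". Protocol 9.2 sets when the disease visits end: "Disease assessments will be performed every 12 weeks until PD". The Amendment 6 summary of changes states that "PRO and MRU collection at Months 12 and 18 in the have been discontinued", so before that amendment collection ran to Month 18 after PD.

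On analysis, SAP Attachment 1 (Medical Resource Utilization) says "Medical resource utilization (excluding study injection administration) will be descriptively summarized by treatment group" and lists what is tabulated, beginning "Frequencies of hospitalization, outpatient visits, type of hospitalization or outpatient visit", followed by reasons and durations. Protocol 11.9 is no more specific: "Medical resource utilization will be summarized descriptively by treatment group. Additional analyses may be conducted", with details left to a separate report. Protocol 9.6 gives the purpose: the data will be "used to conduct exploratory analyses that may be used to support the value story and cost-effectiveness modelling for market access".

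None of these places names a time denominator, a split at PD, a common post-PD window or a rule for incomplete observation. The same SAP attachment builds exposure-adjusted incidence rates for adverse events, and its section on additional time-to-event analyses says that adverse events need adjustment when exposure times differ. MRU gets no such adjustment.

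**The concern.** MRU observation ends about 6 months after PD (18 months before Amendment 6). Treatment is expected to move PD, so it also moves the end of observation. The arm that progresses earlier contributes fewer observed months, and the months it loses are post-PD months, when subjects may be on myeloma treatment.

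Two things follow for totals by arm. They mix the rate of use with the length of observation. They also mix pre-PD and post-PD time in different proportions in the two arms. A reader who takes the table as a comparison of resource use would see active monitoring (Arm A) understated relative to daratumumab (Arm B). That matters because the stated purpose includes cost-effectiveness modelling, where the burden of care after PD is one of the quantities of interest.

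**Working it through.** **Inputs.** Median PFS 30 months (Arm A) and 48 months (Arm B), hazard ratio 0.625, 24-month accrual plus 24 months of follow-up, 180 per arm (Protocol 11.2). End of study about 96 months after first randomization (Protocol 17.9.1). Post-PD collection w = 6 months now (Protocol 9.6) and 18 months before Amendment 6.

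**Assumptions added here.** Exponential PFS, uniform entry, no dropout, and death before PD treated like PD.

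**Check of the PFS model.** The documents give no MRU figure, so the check is on the PFS design. Events = 4(1.960 + 1.036)² / (ln 0.625)² = 163, against 165 stated (the protocol says that the interim analysis is taken into account). With 165 events, power is 85.5%, against at least 85% stated.

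**Observation time.** For a subject with potential follow-up C > w and hazard λ = ln 2 / median, expected MRU time is w + (1 − exp(−λ(C − w)))/λ, averaged over entry. λ is 0.02310 in Arm A and 0.01444 in Arm B.

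*48-month cutoff, w = 18* (C runs from 24 to 48, so C − w runs from 6 to 30):

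- Arm A: mean of exp(−λ(C − w)) = (0.8706 − 0.5000)/(24λ) = 0.668; time = 18 + 0.332/0.02310 = 32.4 months.
- Arm B: mean = (0.9170 − 0.6484)/(24λ) = 0.775; time = 18 + 0.225/0.01444 = 33.6 months.

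All cases, in months per subject:

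| Cutoff | Post-PD collection | Arm A | Arm B | B/A |
|---|---|---|---|---|
| 48 | 18 months | 32.4 | 33.6 | 1.04 |
| 48 | 6 months throughout | 27.4 | 30.1 | 1.10 |
| 96 | 18 months throughout | 51.7 | 60.4 | 1.17 |
| 96 | 6 months throughout | 42.1 | 52.7 | 1.25 |
| 96 | 18 until Amendment 6, then 6 | 49.9 to 50.9 | 58.6 to 59.6 | 1.17 |

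**Last row.** Amendment 6 is dated 9 September 2024 and followed the primary analysis. The original protocol is dated 19 July 2017, so Amendment 6 came at most about 86 months after first randomization. The Amendment 2 entry in Protocol 19 puts the second safety review at about March 2019, six months after the first. The first review needed 60 subjects followed for 8 weeks, so randomization had begun by about July 2018, which gives at least about 74 months. The row is a simulation over that range: a subject contributes Month 12 or Month 18 only if that visit falls before the amendment.

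**Effect on totals.** Let r be the ratio of the post-PD to the pre-PD rate of use. Crude A/B = (pre_A + r·post_A)/(pre_B + r·post_B). The documents do not give r, so it is varied. At 96 months with w = 18, pre-PD time is 36.99 (A) and 48.56 (B), and observed post-PD time is 14.75 and 11.86.

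- r = 1: 51.74/60.42 = 0.86, where the true ratio is 1.00.
- r = 2: (36.99 + 29.50)/(48.56 + 23.72) = 0.92. With complete follow-up to 84 months, post-PD time is 47.01 and 35.44, and the ratio is (36.99 + 94.02)/(48.56 + 70.88) = 1.10.
- r = 5: 1.03, against 1.20 with complete follow-up.

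The 18-then-6 schedule also gives 0.92 at r = 2.

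Arm A totals equal Arm B totals at r = (pre_B − pre_A)/(post_A − post_B). At 96 months (w = 18) this is 11.57/2.89 = 4.0. At 48 months (w = 18) it is (27.87 − 24.20)/(8.16 − 5.72) = 1.5. Above these values Arm A shows more use.

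**Would one pooled rate do?** No. At r = 2 and 96 months, events per person-month over the whole observed period give A/B of 1.04 (w = 6) to 1.07 (w = 18), against 1.10 with complete follow-up, because the mix of pre-PD and post-PD time still differs by arm.

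**The case against.** The strongest counter-case is that this is a descriptive table in an exploratory attachment, with no hypothesis and no place in the testing hierarchy. The protocol allows further analyses in a separate report, and any cost-effectiveness model would presumably be built there. That stands, and it limits the weight of the point.

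At the primary cutoff the gap in observation time is only about 4%, because the 18-month schedule then applied. That also stands. The SAP's latest amendment is dated December 2020 and could not have anticipated the shorter window of Amendment 6, so the change of window concerns mainly the end-of-study addendum.

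The word used for the counts, frequencies, may mean subjects or events. The issue survives either reading. At an assumed constant rate of 0.2 per patient-year in both arms, the share of subjects with at least one event at 96 months (w = 18) would be about 55% in Arm A and 60% in Arm B.

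A reader might infer that active monitoring will look cheaper, or will show fewer encounters. The documents do not support that. The SAP tabulates use and not cost, and the ordering depends on r: at the primary cutoff, Arm A shows more use once r exceeds about 1.5. A reader might also take 25% as the size of the gap. That figure applies the 6-month window to everyone from the first randomization, which is not the schedule that ran.

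**Conclusion.** The point holds as a bias in the by-arm summary, of moderate size and limited consequence. MRU observation depends on progression, and the planned tables ignore this. Arm B is observed about 4% longer at the primary cutoff and about 17% longer at the end of study; 25% is an upper bound.

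Crude totals understate Arm A relative to Arm B at every r tried from 1 to 5. A reversal of order is possible (0.92 against 1.10 at r = 2 and 96 months) but not established, since r is unknown.

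The figures rest on exponential PFS at the design medians, no dropout, and death treated like PD. The last is a simplification: Protocol 11.2 expects about 107 deaths by study end, and subjects who die have neither a post-PD period nor 84 months of follow-up. The complete-follow-up ratios should be read with that in mind. The end-of-study figure also assumes that Amendment 6 took effect 74 to 86 months after first randomization. No efficacy conclusion is touched.

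**What to change.** In SAP Attachment 1 (Medical Resource Utilization):

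- Report hospitalizations, hospital days and outpatient encounters per person-month of MRU collection, by arm, and state whether counts are of subjects or of events.
- Report randomization to PD and post-PD separately.
- Show MRU observation time per arm for each period, and state the data cutoff.
- Use post-PD Months 0 to 6 as the main post-PD window, since it is common to subjects before and after Amendment 6. Report Months 7 to 18 as a separate interval with its own person-time, so that the data already collected are used.
- Note that the post-PD tables describe progressors only and are not a randomized comparison.

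The cost is a change of SAP wording before the end-of-study addendum and slightly more programming, using dates already in the database. Precision in the Month 7 to 18 interval will be low.
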